2. RESEARCH PLAN

Purpose of Study:
To compare scar infiltration with 0.5-1% Lidocaine at a dose of 3 mg/kg (max dose 300 mg) or scar deactivation with acupuncture surface release technique to determine which is more effective in reducing pain in adult patients with chronic, post-surgical pain related to the site of incision after low transverse Cesarean section compared to standard of care physical therapy with the McKenzie Method.
Hypotheses, Research Questions, or Objectives:

 • Objective 1: Compare whether a scar infiltration protocol with Lidocaine is more effective than scar deactivation with acupuncture surface release technique at improving pain in adults with chronic, post-surgical pain related to low transverse Cesarean section incision. • Null Hypothesis 1: 0.5-1% Lidocaine at a dose of 3 mg/kg (max dose 300 mg) does not reduce pain outcomes acutely and over time. • Null Hypothesis 2: Scar deactivation with acupuncture surface release technique does not reduce pain outcomes acutely and over time. • Alternative Hypothesis 1: 0.5-1% Lidocaine at a dose of 3 mg/kg (max dose 300 mg) reduces pain outcomes acutely and over time. • Alternative Hypothesis 2: Scar deactivation with acupuncture surface release technique reduces pain outcomes acutely and over time.
Significance:
According to CDC 2015 data, 32% of all births are delivered via Cesarean section ¹ . In patients who undergo Cesarean section, studies estimate 7-18% will experience chronic post-operative pain at the site of their incisional scar ² . These statistics indicate that up to 1 in 6 out of every pregnancy is at risk of developing postoperative pain with an increased risk with each subsequent Cesarean section, and a significant portion of these members will seek care in the primary care clinic.
Military Relevance:

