In 2016, the Department of Defense employed 1,288,596 active duty service members, of which 15.9% were women ³ . This age range is consistent with peak childbearing age, which extrapolates to a large portion of the female active duty force with the potential to have children during their military careers. Determining whether Scar infiltration or scar deactivation is more effective treatments for the reduction of chronic, post-surgical low transverse Cesarean section pain in military beneficiaries would result in less: lost duty days, profiles, and physical fitness testing exemptions in our active duty population, as well as an improved quality of life for all DoD beneficiaries. Scar infiltration is a technique using high dose and high volume lidocaine to infiltrate the scar. Scar infiltration uses 40cc to 60cc of 0.5% to 1% lidocaine, which is injected throughout the scar with a goal of 3-4mg/kg per injection. Typically a series of 4 to 5 injections. Scar deactivation is a technique when acupuncture needles are inserted into the skin surrounding the scar and are left in place for approximately 20 minutes and then removed. This can be repeated multiple times.

Background and Review of Literature:

Existing Knowledge: The etiology of chronic, post-surgical abdominal wall and/or pelvic pain after Cesarean section has multiple hypotheses. These possible sources include development of intra-peritoneal adhesions restricting fascial planes, anterior cutaneous nerve entrapment, and disruption of the autonomic nervous system within the intracellular fluid matrix known as an “interference field”^{2,4,5,6,7}. While there is not a clearly established and widely accepted pathophysiological cause to this post-operative pain, studies have estimated that between 7-33% of patients experience chronic peri-incisional pain after Cesarean section with Pfannenstiel incision – a type of abdominal surgical incision that allows access to the abdomen and the most common method for performing Cesarean sections today – defined as pain persisting beyond the period of expected healing, approximately 3 months^{2,7}.

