 - Alternating placement of Spring Ten (0.30x40 mm) acupuncture needles to surround scar left in place for a treatment duration of 20 minutes. Needles will be placed at intervals of 1cm to 1.5 cm and will surround the scar with a maximum of 20 needles per treatment.
 - **Group 2: Scar Infiltration with 0.25-1% Lidocaine:**
 - Will consist of calculation of 3 mg/kg dose of 0.5-1% Lidocaine and a dermal followed by subcutaneous injection using 1.5 inch 25 G needle and syringe appropriate for volume based on calculated dose.
 - **Group 3: Physical therapy:**
 - Will be a referral to physical therapy specifying McKenzie protocol treatment for the presenting complaint. The McKenzie protocol is a form of standard of care physical therapy in which the physical therapist tries to find a cause and effect relationship between the positions the patient usually assumes while sitting, standing, or moving, and the location of pain because of those positions or activities. The therapeutic approach requires a patient to move through a series of activities and test movement to gauge the patient's pain response. The approach then uses that information to develop an exercise program designed to centralize or alleviate the pain.

Visit 1 (may be same day as screening visit) (visit window plus or minus 1 week):

Group 1: Scar Deactivation Surface Release Technique protocol (acupuncture):

- Study staff will reconcile medication list (including analgesic medication currently taking).
- Subjects will be weighed (in pounds-not stated weight).
- We will ask what the subjects' expectations are regarding acupunctures effectiveness for chronic, post-surgical pain related to low transverse Cesarean Section.
- The Research Coordinator will record the number of needles placed and the name of the provider performing the acupuncture.
- **Pre-Treatment:**
 - Defense and Veterans Pain Rating Scale (DVPRS)
 - Instruct patients to mark general area of scar on pictures provided on the Patient and Observer Scar Assessment Score (POSAS) Patient Scale.
 - Instruct the PI or AI to complete the POSAS Observer Scale.
- **Post-Treatment:**
 - DVPRS
 - Instruct patients to mark general area of scar on pictures provided the POSAS Patient Scale.
 - Instruct the PI or AI to complete the POSAS Observer Scale.

Group 2: Scar Infiltration with 0.25-1% Lidocaine:

- Study staff will reconcile medication list (including analgesic medication currently taking).

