- Subjects will be weighed (in pounds-not stated weight).
- We will ask what the subjects' expectations are regarding lidocaine's effectiveness for chronic, post-surgical pain related to low transverse Cesarean Section.
- The Research Coordinator will document the total volume of 0.5-1% Lidocaine injection.
- **Pre-Treatment:**
 - DVPRS

- Instruct patients to mark general area of scar on pictures provided on the POSAS Patient Scale.
- Instruct the PI or AI to complete the POSAS Observer Scale.
- Post-Treatment:
 - DVPRS
 - Instruct patients to mark general area of scar on pictures provided the POSAS Patient Scale.
 - Instruct the PI or AI to complete the POSAS Observer Scale.

Group 3: Physical Therapy:

- Study staff will reconcile medication list (including analgesic medication currently taking).
- Subjects will be weighed (in pounds-not stated weight).
- We will ask what the subjects' expectations are regarding physical therapy's effectiveness for chronic, post-surgical pain related to low transverse Cesarean Section.
- Subjects will be given a study diary and asked to track the dates and duration of their physical therapy treatments.
- DVPRS
- Instruct patients to mark general area of scar on pictures provided on the POSAS Patient Scale.
- Instruct the PI or AI to complete the POSAS Observer Scale.

Visit 2 (4 weeks after visit 1 (visit window plus or minus 1 week)):

Group 1: Scar Deactivation Surface Release Technique protocol (acupuncture):

- Study staff will reconcile medication list (including analgesic medication currently taking).
- Subjects will be weighed (in pounds-not stated weight).
- The Research Coordinator will record the number of needles placed and the name of the provider performing the acupuncture.
- Pre-Treatment:
 - DVPRS
 - Instruct patients to mark general area of scar on pictures provided on the POSAS Patient Scale.
 - Instruct the PI or AI to complete the POSAS Observer Scale.
- Post-Treatment:
 - DVPRS
 - Instruct patients to mark general area of scar on pictures provided the POSAS Patient Scale.
 - Instruct the PI or AI to complete the POSAS Observer Scale.

Group 2: Scar Infiltration with 0.25-1% Lidocaine:

- Study staff will reconcile medication list (including analgesic medication currently taking).
- Subjects will be weighed (in pounds-not stated weight).
- The Research Coordinator will document the total volume of 0.5-1% Lidocaine injection.
- Pre-Treatment:
 - DVPRS

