Describe the method that will be used to create and assign unique study codes to data.	The unique study code will be assigned in sequential order beginning with 001 at each recruiting site. Subjects at Nellis AFB will be named such as NE001 and subjects at Scott AFB will begin with SC001. The code will be placed in a Master Key of identifiable PHI/PII for each subject at each collaborating site					
Describe the method that will be used to create and assign unique study codes to specimens.	 N/A, not collecting specimens					
What is the format of the key?	 Electronic					
Who will have access to the key?	Principal Investigator and/or Designated Research Coordinator at each study site					
Where will the key be stored and how will it be protected?	
Location(s): Each collaborating site will maintain a Master Key of identifiable PHI/PII that will be kept in an electronic database separate from the coded, de-identified research data, which will be encrypted, password protected and the access will be restricted to the PI and/or Designated Research Coordinator. The Master Key will not be stored on any non-government or personal computers or laptops. At the conclusion of the study, the data from each site will be de-identified prior to review and analysis.
 
Confidentiality measures: The coded research data will be kept in a locked cabinet in a locked office and only the research department has the key. The coded research data will be retained until the conclusion of the research study. Once a Final Report has been approved by the IRB, all the paper records will be de-identified and any key linking the subject to their records will be destroyed, based on AFI 33-332, "The Air Force Privacy and Civil Liberties Program" and the National Institute of Standards and Technology Special Publication (NIST SP 800-88) for the approved methods to destroy PII. The anonymized research data will not be utilized for further research activity beyond the protocol stipulations without additional IRB approval.
					

Complete the table.

Source of Research Material per Participant (Procedures)	# Routine Care	# Research Driven	# Total Procedures
DVPRS	0	9	9
POSAS	0	9	9
Acupuncture	0	4	4
Lidocaine	0	4	4

McKenzie Protocol	0	4	4
g. Instrumentation: N/A			

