----------------------------	--	------------------------------	--

Participation Compensation: Subjects will not be paid for participation in this study.

Assent Process: N/A

Benefits:

Subjects may experience an improvement in pain in both the treatment groups; however, this is not a guarantee.

Risks:

The potential risks to participate in this study are minimal. The risks associated with participating in this research study include:

Acupuncture Risks:

- Likely and not serious:
 - Pain
 - Bleeding
- Less Likely and not serious:
 - Infection
 - Muscle cramps/spasms
- Less Likely and serious:
 - Bowel Perforation
 - Transient vasovagal response to needling

Lidocaine Risks:

- Likely and not serious:
 - Pain
 - Bleeding

- Less Likely and not serious:
 - Infection
 - Lidocaine toxicity

These risks will be minimized by cleaning the treatment site with an alcohol swab prior to placement. If at any time the patient reports a side effect, they will be referred to one of the Investigators for care. There may be a risk of inadvertent breach of confidentiality.

Costs: N/A

Safeguards for Protecting Information:

The research consents and HIPAA Authorization Documents will be stored in a locked cabinet in a locked room with restricted access. All identifiable research data including patient demographics will be kept in an electronic database separate from the coded research data, which will be encrypted, double password protected and the access will be restricted. The research data will be coded and any links to identifiable data (i.e., Master Key) will be destroyed as soon as all data mergers have occurred, or no later than at the closure of the study, all identifiable patient information will be destroyed based on AFI 33-332, "The Air Force Privacy and Civil Liberties Program" and the National Institute of Standards and Technology Special Publication (NIST SP 800-88) for the approved methods to destroy PII. The anonymized research data will not be utilized for further research activity beyond the protocol stipulations without additional IRB approval. At the conclusion of the study, the data will be de-identified prior to review and analysis.

Data and Specimen Storage Plan

How will coded or identifiable data/specimens be stored?

	Paper data, including completed consent forms	The research consents and HIPAA Authorization Documents will be stored in a locked cabinet in a locked room with restricted access.

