	Electronic data	Medical records will be annotated with ICD-10 code Z00.6 to reflect the subject's participation in a research study, in which they are receiving a research-related treatment intervention. All research data that includes the Master Key of identifiable patient demographics and PHI/PII will be kept in an electronic database at each site, separate from the coded research data, which will be encrypted, password protected and the access will be restricted.
	Long-term storage (following completion of the study and inactivation of IRB approval)	The research data will be coded and any links to identifiable data will be destroyed (an approved shredding bin) as soon as possible or no later than at the closure of the study, with the exception of those study subjects that consent to place their de-identified research data into the "Nellis Acupuncture Research Data Repository (FWH20140048H)" for future research. The anonymized research data will not be utilized for further research activity beyond the protocol stipulations without additional IRB approval. All de-identified research data will be maintained for 3 years following study closure.

Safeguards for Protecting Subjects Relative to Reasonably Expected Risks:

Safeguards are in place for protecting subjects and their health data. The research consents and HIPAA Authorization Documents will be stored in a locked cabinet in a locked room. If at any time the patient reports a side effect, they will be referred to one of the Investigators for care.

Categories of subjects: None

Clinical Care:

All subjects will receive standard of care regardless of inclusion into this study. If at any time a subject experiences any injury or adverse effects, appropriate clinical care will be given or subject will be referred to appropriate provider.

Injury Compensation: N/A

Data Safety Monitoring:

N/A – none of the situations listed above apply

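### Group 2's dosing instruction omits the 300 mg maximum, its record holds volume but not concentration or mg, and the listed harms other than pain have no visit item or planned summary

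*Combined protocol and SAP*

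**What the plan says.** **Dose.** The purpose statement and hypotheses in Section 2 specify "0.5-1% Lidocaine at a dose of 3 mg/kg (max dose 300 mg"). The instruction for Group 2 under Randomization in Section 3 reads "Will consist of calculation of 3 mg/kg dose of 0.5-1% Lidocaine" and does not repeat the maximum. The Group 2 headings there and at each visit give the strength as 0.25-1%.

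**Exposure record.** At each of Visits 1-4 the Group 2 list has one lidocaine item: "The Research Coordinator will document the total volume of 0.5-1% Lidocaine injection". Measured body weight in pounds is on the same lists. Concentration and milligrams are not.

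**Harms.** The Risks part of Section 4 lists pain, bleeding and infection for both needle treatments. It adds lidocaine toxicity for lidocaine, and muscle cramps or spasms, bowel perforation and vasovagal response for acupuncture. The stated handling is: "If at any time the patient reports a side effect, they will be referred to one of the Investigators for care". None of the visit lists in Section 3 has a side-effect item. The procedure table in Section 3 lists only DVPRS, POSAS and the three treatments. Section 6 names no harm or exposure summary.

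**The concern.** The treatment under test is defined in mg/kg with a ceiling in mg, but the place where staff read how to give it omits the ceiling, and the place where they record it leaves out the quantity the ceiling applies to. A site following Section 3 to the letter could exceed the protocol's own maximum in a heavy subject. At analysis, nobody could show from the research data that Group 2 received the dose named in Null Hypothesis 1 without assuming it.

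The harms gap has a similar form. Two needle treatments are compared with physical therapy. The protocol text would give efficacy results for all three arms but no count by arm of bleeding, infection, lidocaine toxicity or the other listed events, because no variable is collected from which to make one.

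**Working it through.** The plan gives no figure to reproduce. The check is unit arithmetic, followed by a comparison of the harm list with what is collected.

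**Inputs.** Dose 3 mg/kg and cap 300 mg (Section 2); strength 0.5-1% in the text and 0.25-1% in the headings (Section 3); four lidocaine sessions per subject (procedure table, Section 3); 60 planned to enrol, 48 to complete, and a calculated requirement of 45 (Section 6). Equal allocation to the three arms is assumed.

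**1. Literal instruction against the cap.** 300 mg / 3 mg/kg = 100 kg (about 220 lb). Above that weight an uncapped 3 mg/kg exceeds the maximum: 110 kg gives 330 mg; 120 kg gives 360 mg, which is 60 mg or 20% over. The eligibility criteria set no upper weight.

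**2. What volume shows about the cap.** mg = mL × concentration (%) × 10. The cap is reached at 300/5 = 60 mL for 0.5% and at 300/10 = 30 mL for 1%.

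- Up to 30 mL: cap kept at any strength from 0.5% to 1%.
- Above 60 mL: cap broken at any of those strengths.
- Above 30 and up to 60 mL: depends on the strength, which is not recorded.

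If the 0.25% in the headings is allowed, the upper end moves to 300/2.5 = 120 mL.

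**3. Which correct doses fall in that window.** A correct 0.5% dose is 3/5 = 0.6 mL/kg, so it lies in the window for every subject above 30/0.6 = 50 kg and up to 60/0.6 = 100 kg (about 110-220 lb). A correct 1% dose is 3/10 = 0.3 mL/kg, at most 30 mL up to 100 kg, and so shows that the cap was kept.

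**4. What weight adds.** With weight, the ratio of mL to kg can be formed: 0.6 fits 0.5% and 0.3 fits 1%. That identifies the strength only if the dose was calculated and drawn up correctly. Example at 80 kg with 48 mL recorded:

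- at 0.5%: 48 × 5 = 240 mg, 240/80 = 3 mg/kg, within both limits;
- at 1%: 48 × 10 = 480 mg, 480/80 = 6 mg/kg, above both limits.

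The two records are identical.

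**5. Harms.** Pain is measured by DVPRS before and after treatment in Groups 1 and 2 at Visits 1-4, as an efficacy score. Bleeding, infection, lidocaine toxicity, cramps or spasms, bowel perforation and vasovagal response have no item at any visit.

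**6. What a harm table could show.** With no events in n subjects, the exact two-sided 95% upper limit is 1 − 0.025^(1/n):

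- n = 20 (60/3): 16.8%
- n = 16 (48/3): 20.6%
- n = 15 (45/3): 21.8%

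Such a table can describe, but it cannot support comparison between arms.

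**The case against.** The strongest reply is that the cap is in the protocol: Section 2 states it in the purpose and the hypotheses, and Section 3 does not revoke it by failing to repeat it. Weight is recorded, so most volumes can be reconciled with a strength. The 480 mg case needs an error against the instruction, and staff unaware of it could write the wrong strength in a new field too. Section 12 lists Procedure Instructions and a drug-use form (Form O), not shown here, which are natural places for preparation and recording rules.

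Much of this stands, and it bars several stronger readings that a reader might infer:

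- **That the dose is unknowable.** It is not: weight gives a partial check. What is missing is a check that does not presuppose the answer.
- **That Section 2 contradicts itself on dose.** The phrase "which is injected throughout the scar with a goal of 3-4mg/kg per injection" describes the technique in general, as background. It is not a trial instruction.
- **That harms would go unnoticed.** Reported side effects lead to care, medications are reconciled and the scar is examined at every visit, and medical records are annotated for study participation. None of these is a harm record by arm, but they do not suggest neglect.
- **That the Data Safety Monitoring entry shows events go unrecorded.** The answer "none of the situations listed above apply" is a form response whose list of situations is not shown. It concerns monitoring and says nothing about what is recorded.
- **That destroying the key rules out chart look-up.** Section 3 ties this to approval of the final report. Section 4 says links "will be destroyed as soon as all data mergers have occurred, or no later than at the closure of the study". Look-up remains possible during data collection.
- **That the efficacy results are compromised.** The planned DVPRS and POSAS tests do not use the mg given or the harm counts.

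Section 6 does plan frequency distributions for nominal variables, so recorded events could be tabulated. The difficulty is that the protocol text records none.

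**Conclusion.** The point holds for the protocol text. The operative Group 2 instruction omits the 300 mg maximum and, read literally, exceeds it above 100 kg. Two strength ranges are in use. For volumes above 30 and up to 60 mL, which include every correct 0.5% dose above 50 and up to 100 kg, adherence to the cap and to 3 mg/kg rests on assuming correct preparation. Listed harms other than pain have no visit item and no planned summary.

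The number of sessions affected cannot be derived. It depends on the strength used and on body weights, and the documents give neither. The ceiling is all lidocaine sessions: 20 subjects × 4 = 80, assuming 60 enrol in equal arms. Nothing here shows that an overdose would occur. The conclusion also depends on the unseen attachments not already containing the cap and the recording rules; if they do, the remaining work is to bring them into the protocol and add the summary. This should be corrected for subject safety and for a verifiable description of the treatment. It does not invalidate the efficacy analysis.

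**What to change.** 1. **Section 3, Randomization, Group 2:** state the 300 mg maximum beside the 3 mg/kg rule, and use one concentration range in all headings and text.
2. **Section 3, Visits 1-4, Group 2:** record concentration, volume, mg and mg/kg (kg = pounds / 2.205). Confirm before injection that the dose is at most 3 mg/kg and at most 300 mg. Taking the strength from the vial label makes a mix-up less likely to pass, though no field excludes it.
3. **Section 3, all groups, Visits 2-5:** ask one identical question about side effects since the last visit. In Groups 1 and 2, also note events during the session at Visits 1-4. Enter both on the coded form.
4. **Section 6:** add one descriptive table by arm giving subjects and events against the Section 4 list, with exact two-sided 95% limits. For Group 2, add the distribution of mg and mg/kg and the number of sessions above the cap. Show session events separately and make no between-arm test.

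**Cost.** Extra fields at up to 80 lidocaine sessions, up to 60 × 4 = 240 short side-effect records, up to 40 × 4 = 160 session notes, and one table. No added visits or staff. More minor events will be reported, and session events in the needle arms will not be comparable with physical therapy, which has no study-delivered session.
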